#### Qualitative study

To explore and explain findings from the review and the survey, we will carry out additional qualitative data collection. This will involve three **focus group discussions** (FGDs) per country focussing on:

- 1. *Patients/carers* to help us to understand what SCD patients/carers need and expect from care, their perceptions of the quality of care received, their ideals for "patient-centred SCD care", and constraints they face in accessing care.
- 2. *Community members* more broadly (religious and other community members, traditional healers, other influential community members) to establish localised understanding of SCD and perceptions around community access to health facilities.

<sup>† We are planning to follow this with research into how best to support journalists to engage more effectively with SCD patients and researchers. We will also apply for separate ethics for this activity.

3. *Health facility staff* providing SCD care to establish standards of care currently in place, typical approaches in SCD care, their views on what "patient-centred SCD care" would entail, and perceptions around quality of SCD care and areas for improvement (see Appendix 1 for FGD guides).

**Key informant interviews:** 5–10 will take place with policymakers who play a role in SCD and community health decision-making in order to determine which policies guide SCD in each country, resource allocation for SCD care, and higher-level facilitators and barriers of SCD care. These key informants may include Directors of Clinical Services/Public Health and National/Zonal Blood Services and senior facility and university officials responsible for training in SCD care (e.g. Medical Directors, Deans). We will also carry out key informant interviews with representatives from community-based or national-level organisations supporting patients with SCD and carers of children living with SCD to understand their perspectives around uptake of care, common misconceptions, patient-centredness in SCD care, and facilitators and barriers of uptake and delivery of quality SCD care.

Findings from the situational analysis will by synthesised and shared with PAC and SBA teams as a springboard for discussion and to inform priority topic areas for each group.

#### Realist evaluation

Information from the literature, media, and policy reviews and the qualitative study will be synthesised and analysed retroductively, applying "realist logic"—we will look for relationships in any data that speak to patterns around the provision and uptake of patient-centred, evidence-based SCD care. In particular we will generate hypothesised "context, mechanism, outcome configurations" and will hypothesise what we think within the *context* is likely to drive (as in, what will our participants be likely to respond to in the intervention and why—these are the *mechanisms*) patient-centred, evidence-based SCD care, and what the *outcomes* of that will be. We will then develop a programme theory from combining these "context-mechanism-outcome configurations". We will reflect on this theory within our study team (as each country Principal Investigator and other members of the study team are instrumental in driving SCD in each country) and a selection of stakeholders (community and clinical) in a half-day *participatory workshop* and refine it to develop an **initial programme theory.** 

#### Intervention start-up

Simultaneously during this phase, we will be **recruiting health facilities** in our three study areas (6 facilities/country) **and building SBA and PACs teams** associated with these facilities (1 each/facility = 6 SBA teams total per country) and community (6 PAC teams total per country). We will also begin capacity strengthening with each team. In each country, a SBA and PAC lead will be appointed. These individuals will recruit and capacitate SBA and PAC teams and support their activities through mentoring and coaching.

Throughout all aspects of implementation across phases, we will carry out **detailed documentation of processes**, which will feed into the realist evaluation. In this phase, processes of facility and community entry will be documented, as will all capacity strengthening activities, *including study team reflections* on challenges and opportunities around capacity strengthening.

#### Phase 2: Intervention and study of its implementation (months 18-42)

To overcome barriers identified in Phase 1—and perhaps others that might be raised by each team—solutions to early identification and uptake of SCD care will be identified and tested through **repeated PACs** with teams of SCD patients/carers and other influential community members, and **SBA cycles** will be carried out with health facility teams to drive routine use of evidence-based SCD care, centred around clinical mainstays. Finally, PAC and SBA teams will be brought together in learning collaboratives to **co-create guidance for patient-centred SCD care**.

#### Documentation of processes

Again, there will be detailed documentation of processes throughout, often accompanying by structured observation (either carried out by trained research assistants or PhD students) guided by a template. This will include:

- PAC team members/turnover
- Details of capacity strengthening activities for each member
- PAC meetings: attendees, main discussion points, decisions made
- Outcomes of PACs: changes resulting
- SBA team members/turnover
- Details of capacity strengthening activities for each member
- SBA meetings: attendees, main discussion points, decisions made
- Outcomes of PACs: changes resulting in standards of care

In particular, meeting discussion points and decisions will be a rich source of data about challenges and facilitators around the aim of each cycle. With member permission, these meetings will be recorded and transcribed. Detailed **observation notes, transcripts of meetings, and reflections from the SBA and PAC leads from reflective implementation diaries** will be generated and collated on a monthly basis (see Appendix 1 for some of these tools). Additionally, PAC and SBA **team documentation** (meeting minutes, any graphical information or tables outlining the outcomes of their activities) will also be reviewed by the SBA and PAC leads and photographed/scanned to ensure a digital record is kept.

In addition, **learning collaboratives will be recorded** in detail, collecting similar content as meetings including attendees, key discussion points, and decisions made. Prominent and promising solutions will be described, as well as those that tried and failed. Structured observation templates will guide data collection during learning events. Some discussions will, with permission, also be recorded and transcribed.

**Mentoring and coaching** will be facilitated by guidance of what to review with each team (e.g. actions taken, progress made, challenges, successes) with space for commentary. These will be collated on a monthly basis. **PACTS study team meetings** will also be recorded and minutes will be taken. These meetings—and mentoring and coaching guidance—will be a good opportunity for the SBA and PAC leads to offer their reflections and insights on the processes.

All of these data will provide comprehensive insights around many of our study questions.

Outcomes from the PAC and SBA activities, for example, changes in indicators that reflect the clinical mainstays (e.g. number of outpatient visits and inpatient days; haemoglobin levels; number of infections and transfusions/year) will also be independently evaluated by our study team in an ongoing epidemiological study which is described in a separate protocol.

#### Realist evaluation

Throughout this phase, the objective of the realist evaluation is to test and refine the initial programme theory from Phase 1. This programme theory will underscore the relationship between PACs and SBA activities, how participants respond to them, what outcomes they produce, and how the process and outcomes are moderated by contextual factors. To test and refine the "context-mechanism-outcome" configurations originally generated, additional data alongside the process data from above will be collected and analysed in three "rounds" *at months 18, 30, and 42*.

Data will include *qualitative data* from PACs and SBA participants and other key stakeholders about their activities and perceptions and *contextual* data (e.g. collating documents such as relevant policies and national strategies, health management plans, documentation of health facility changes).

**Qualitative data** will include an FGD with each PAC team and SBA team (12 FGDs per country per round) and 5-10 in-depth interviews with other stakeholders (e.g. leaders of each participating health facility, relevant blood services staff, community leaders who may not be part of the PAC team, SCD community-based organisation representatives) (see Appendix 1 for tools). The intention of these will be to generate insights around what is working (or not) through the PACs and SBA cycles and why. Insights around contextual factors moderating each teams' activities will also be garnered. In-depth interviews will also be carried out with the SBA and PAC lead.

Additional **contextual data** will be updated monthly, but summarised and analysed against other data within each round. It is likely that PAC and SBA team members may be able to provide these insights, but if not, a check-in with the facility in-charge or local leaders may be needed. As these stakeholders are very likely to be interviewed as part of the qualitative data collection, additional questions about contextual factors may be added there. These data will include: information about each participating health facility (e.g. changes to staffing, infrastructure, availability of medicines or equipment that may affect SCD care); policy changes; broader social/cultural changes or events (e.g. conflict, an election); and any other factors that arise that the study team feels might impact upon either the implementation of the interventions, or their outcomes on SCD care uptake and provision.

Process, qualitative, and contextual data will be synthesised in each round of data collection. Again, realist logic will be applied and we will explore the data retroductively. The aim will be to test and refine the context-mechanism-outcome configurations and, ultimately, the programme theory that results. This will always be done through participatory workshops with the study team and key stakeholders—as for the initial programme theory.

#### Phase 3: Knowledge translation and close-out (months 42-48)

In this final phase, three "rounds" of the realist evaluation will have been completed, after which a **final, transferrable programme theory** will be generated for each country to highlight how and under which conditions SBA and PACs can be used together to drive patient-centred, evidence based SCD care provision and uptake. Importantly, this final programme theory will be compared/tested across all three countries for homogeneity (meaning that it is robust and "holding up" across three very different contexts) or heterogeneity (likely highlight the role of critical moderating contextual factors unique to each country). This programme theory—or its iteration from each country—will be of use to other research or implementation teams seeking to replicate this intervention elsewhere.

However, key insights gained through the processes of the PACs and SBA themselves and the most successful solutions generated will be packaged into policy briefs (or other relevant outputs as decided by the consortium—possibly with inputs from journalists (see footnote on page 9)—intended to influence SCD policy. A close-out workshop (year 4) will be held for all PACTS consortium members to collate these findings and to identify key recommendations and appropriate audiences for these. The aim is threefold: i) to support **community health policy change** through guidance that will improve community understanding of SCD, encourage earlier diagnosis and uptake of care, and facilitate access to care; ii) to support the **introduction of standards of care reflecting clinical mainstays** (and supporting guidance on their routine implementation generated from SBA cycles); and iii) to **introduce guidance patient-centred SCD care**, also with guidance around its implementation. Throughout the consortium's lifetime there are embedded dissemination events at which there will be interim updates provided. However, during this final stage a much more intensive push to influence policy change will take place.

Table 1 below summarises the primary data collection throughout phases 1 and 2, as there will be no data collection in Phase 3. Of note is that some of the participants from the situational analysis are likely to be engaged in the intervention and repeated. Therefore, the total number of participants likely reflects an overestimate.

| Data
collection
method | Activity  | Total
participants |
|------------------------------|---|-----------------------|
| Phase I                      |   |                       |
| Baseline
survey           | 300 patients actively receiving care at each of the three main teaching hospitals (one per country); we will aim to find 100 SCD-affected persons/carers of children living with SCD who do not | 900 active patients   |
|                              | access care   | 300 inactive patients |
| Focus group
discussions   | Three per country (community FGD, SCD patient/carer FGD, and SCD healthcare provider FGD), each with 6–8 participants = 18–24 participants per country x3 countries                             | 54–72                 |
| Key informant interviews     | 5–10 per country x3 countries   | 15–30                 |
| Process
documentation     | 
 
Capacity strengthening activities (what took place, where, who attended)
 
Reflections on key gaps and strengths
 
   | N/A                   |

#### **Table 1.** Summary of primary data collection for the study of implementation within PACTS

| Phase II                 |  |           |
|--------------------------|--|-----------|
| Process
documentation | 
 
Detailed log of all activities led by the study team (what took place, when, where, who attended)
 
SBA and PAC monthly meeting minutes
 
SBA and PAC monthly meeting observation notes
 
SBA and PAC monthly meeting transcripts (from audio recordings)
 
SBA and PAC monthly mentoring checklists/comments
 
SBA and PAC run charts/other tables or visuals capturing improvement
 
Learning collaborative observation notes
 
SBA and PAC lead reflective implementation diaries
 
Minutes/recordings from PACTS study team meetings
 
 | N/A       |
| FGDs                     |  |           |
| In-depth
interviews   | 5–10 per round = 15–30 per country
And SBA and PAC lead each round (assume no turnover and
participant repeats)  | 47–92     |
| Contextual
data       | Will be informed by existing qualitative data collection   | N/A       |
|                          | TOTAL  | 1676–1754 |

#### 3.4 Data Analysis

The situational analysis review of activities will draw only from secondary data. We will carry out a thematic analysis to identify core drivers or inhibitors of SCD care provision and uptake. The media review will involve a media content analysis—identifying and summarising core content (key SCD messages shared, misinformation, correct information).

The baseline study will simply generate categorical data. We will use Stata 13 to generate descriptive statistics. Open text responses will be coded and analysed thematically.

For qualitative data (from focus group discussions and in-depth or key informant interviews, as well as transcripts from SBA and PAC meetings or learning collaboratives), we will carry out a framework analysis. The framework will be generated following creation of the initial programme theory and will be designed to collate key aspects of implementation, but also to test context-mechanism-outcome configurations. All coding and analysis will be assisted using NVivo.

Process documentation will be collated and updated in an Excel file for each country, with a sheet generated for each PAC or SBA team to document member activities and turnover and key happenings (from observations or SBA and PAC lead reflective implementation diaries) from each meeting. A separate Excel file will be used to collate mentoring and coaching data. A final file will be used to collate attendance and observation data from learning collaboratives.

#### 3.5 Participant Sampling and Recruitment

The **study areas** for our research cover the catchment populations of the teaching hospitals in Abuja (Nigeria), Kumasi (Ghana) and Lusaka (Zambia). We will liaise with the Ministry of

Health in each country to secure their endorsement for the study. In Nigeria, a representative from the Ministry of Health is part of our external advisory board. We will use invitation/permission letters from the Ministry to support entry into each health facility.

**Six health facilities/country** within these study areas will be selected to participate (with support from the existing SCD community engagement officers in each site). Selection criteria for facilities will include a) they provide care (including blood transfusions) for and have a substantial pool of SCD patients; and b) they represent diversity in location (urban, semi-urban, rural). Study information will be provided to the facility in-charge and after one week, they will have the responsibility of consenting to their facility's participation or declining their facility's participation. As PAC and SBA teams are built based on the facility, these will not be selected until the facilities have been confirmed.

Participants for the patient/carer survey will be identified in two ways. Those who are actively receiving care will be known to the three teaching hospitals that we are working with. Study materials will be posted in the waiting rooms where SCD-affected persons and carers of children living with SCD may wait. Here, members of the study team will also approach prospective participants whilst they wait giving them information about the study and answering questions that they might have. At the conclusion of the visit, if the SCD patient/their carer is willing, an informed consent process will be carried out and they will be guided through a research assistant-administered survey taking no more than 30 minutes of their time. Recruitment will continue until 300 unique SCD patients/ carers of children living with SCD have participated in the survey. For SCD-affected persons/ carers of children living with SCD who are not receiving care, we will work through community-based organisations who provide support around SCD to whom these individuals may be known. Research assistants will identify prospective participants with the help of these organisations and will follow-up participants first by phone and will then arrange to do the survey at their home or at another preferred location. An informed consent process will take place before any data collection begins. We will also deploy snowball sampling with identified participants to determine if they may be aware of other SCD-affected persons/ carers of children living with SCD who are not receiving care. Recruitment will continue until 100 participants who are not receiving SCD care have been identified. For both types of participants (those receiving care, and those not), informed consent will also have provisions should the participant not be literate (see more in section 5.1).

Please note that sample size calculations have not been made, as we are not making statistically significant inferences, but simply carrying out this survey in an exploratory way to gain insights from a broad cross-section of SCD-patients and carers of children living with SCD. At each teaching hospital (one in Abuja, one in Lusaka, one in Kumasi), there are approximately 2000–3000 SCD patients who receive care regularly throughout the year. Given our timeline, we estimate that it would therefore be plausible over a three-month period to obtain survey responses from 300 unique patients/carers. The numbers of SCD-affected persons/ carers of children living with SCD who do not receive care is unknown in all contexts, and we anticipate that it will may be much more challenging to identify these participants, however, their perspectives are incredibly important. As such, we will continue to recruit until we reach 100 unique participants, though this may need to be adjusted down if this is simply not possible within the three months allotted for this survey.

In months 15-18, each PACs team (1/facility) will be drawn from communities within the catchment area of each participating health facility. Each team will comprise SCD patient/carers and influential community members/decision-makers (which may also include traditional healers) for approximately 10 people per team. Inclusion of community members will improve the community's understanding of the challenges faced by SCD patients. Community team members will be accessed first by identifying and liaising with community-based organisations that support SCD-affected persons, who will serve as community gatekeepers in addition to providing suggestions for possible participants. Discussions with community leaders to identify prospective participants as well as snowball sampling (e.g. an identified carer may be aware of another carer in their community) will also take place. Inclusion criteria will be: aged 18 and older (unless a person living with SCD, in which case they must be at least 15 years of age); a carer of someone (alive or deceased) with SCD or someone living with SCD or a community leader or a traditional healer; must be literate; must be willing to consent. Each prospective participant will be approached by the study team and given study materials (the participant information sheet). They will be given at least one week to decide their participation.

Simultaneously, at each participating health facility, all staff with a role in providing SCD care will be invited to participate in a **SBA team** (1/facility). 6-10 members will be selected to maximise diversity in knowledge and experience (e.g. by cadres, years of experience, responsibilities). These staff will be identified by the facility in-charge, and by speaking to staff on relevant units to identify those staff members with SCD responsibilities. Inclusion criteria will be: those staff working for at least one year providing SCD disease, aged 18 and older, speaking English, and consenting to participate. Each prospective participant will be approached by the study team and given study materials (the participant information sheet). They will be given at least one week to decide their participation.

**Key informants** (e.g. ministry officials, medical education leaders, community-based organisation representatives) will be identified through our PACTS consortium's extensive network. Where we may not have knowledge of the right person, most of these individuals will have an online presence for the role that we seek and will be approached accordingly. As for other participants, each prospective participant will be approached by the study team and given study materials (the participant information sheet). They will be given at least one week to decide their participation. Key informant interviews may take place in their office or another private space of their choosing. For informants who might be at a distance, the interviews will be arranged online.

Other **in-depth interview participants** (e.g. other community members, other members of staff at participating health facilities) will be identified as intervention implementation progresses and we learn more about who is influential in community and facility-based SCD issues. They will be approached, as for all other participants, by a member of the study team and given study materials (the participant information sheet). They will be given at least one week to decide their participation.

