#### 1.2 The unmet needs and gaps our study will address

Improving early detection and uptake of care, use of the clinical mainstays for SCD, and patient-centred care will be the focus of our research, as these three areas constrain SCD care in SSA, exacerbating morbidity and mortality.

**Poor early detection and uptake of care:** Failure to diagnose SCD means it is very difficult to provide evidence about the burden and gravity of problem to policy makers so they can implement appropriate programmes. At least 50% of individuals with SCD in SSA are never diagnosed and therefore do not take up care. For example, Nigeria's SCD prevalence is ~4 million among its population of 202 million; only ~30,000 patients (<1%) are registered in health facilities (co-principal investigator ([name]) personal communication).

Consequently, there are very limited data from SSA on morbidity and mortality. In Tanzania, the average life expectancy of SCD patients managed in high-quality facilities is 33 years compared to 52 years among their national healthy peers. The overall mortality rate of 1,725 SCD patients in Tanzania from 2004 to 2009 was 1.9/100 person years of observation and was highest in those under 5-years old (7.3/100 person years). In Nigeria SCD accounts for 5.6% of national under-five mortality. **These deaths rates are similar to those in high-income countries prior to the routine implementation of clinical mainstays for SCD**.

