#### Baseline patient survey

Using information from the scoping review and media content analyses, a baseline survey will be designed and administered to consenting SCD patients aged 15 and older (or, for children, their carers) attending clinics at the teaching hospitals in Abuja, Lusaka, and Kumasi—"active" patients. To understand SCD care provided and perceptions of access to care and quality of care, we will sample 300 participants (either a patient or their carer) in each teaching hospital. The tool will be administered electronically by a research assistant, and built on Microsoft Forms. Responses will be password protected and automatically sent—or queued to be sent—to cloud storage depending on internet connectivity. A similar survey will be administered to individuals with SCD who do not access SCD care from the formal national health service—"inactive patients" (see Appendix 1 for *drafts* of both tools—these will likely change with scoping review/media content analysis inputs). They will be identified through snowball sampling (by peer-SCD patients) and local community-based organisations who support SCD-affected persons. This information will provide a broad understanding of the socio-cultural and health system barriers they face in accessing of SCD care.

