# Situational Analysis: Patient Survey: Inactive Patients

|     | Prompt  | Response   |
|-----|---|--|
| 1   | Date  | [dd/mm/yy]   |
| 2   | Participant ID  | [######]   |
| 3   | Country   | Ghana
Nigeria
Zambia   |
| 4   | Participant/ dependent age at last birthday   | [Age in years]   |
| 5   | Participant/ dependent age of SCD diagnosis   | [Age in months—e.g. three years = 36 months]   |
| 6   | Do other members of
your family have SCD?  | Yes [number]
No
I don't know   |
| 7   | Number of health
facilities at which SCD
care has been sought   | 1
2–3
4–5
More than 5
I don't know
N/A—I have never sought care at a health facility      |
| 8   | Do you feel that it is
important to receive care
for SCD?   | Not at all important
Somewhat important
Very important
Not sure                                 |
| 9   | [If "not at all important",
"somewhat important",
or "very important" to 8]
Can you please explain
why you feel that it is/is
not/is somewhat
important to receive SCD
care? | [Open text]  |
| 10  | Why are you/your
dependent not
undertaking care for
SCD?   | Select all that apply
Costs
Transportation
Permission to access care
Other [please indicate] |
| 11  | What do you feel would
make it easier for
patients to access SCD
care?   | [Open text]  |
| 12  | Do you/your dependent
face stigma or
discrimination as a
result of your/their SCD
diagnosis?  | Yes
No
I don't know  |
| 12a | [If yes to 12]
Please explain why you
stated yes  | [Open text]  |

| 40  | De yey feel that the    | Vee                                     |
|-----|-------------------------|---|
| 13  | Do you feel that there  | Yes                                     |
|     | are misconceptions      | No                                      |
|     | about SCD in your       | l don't know                            |
|     | community?              |   |
| 13a | [If yes to 13] What do  | [Open text]                             |
|     | you think those are?    |   |
|     |                         |   |
|     |                         |   |
| 14  | Have you/your           | Yes                                     |
|     | dependent ever received | No                                      |
|     | care for SCD?           | l don't know                            |
|     |                         |   |

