#### Situational Analysis: FGD with Community Members

Introduce yourself, explain the purpose of the FGD, take informed consent. Remind participants about confidentiality.

- 1. Please describe what you understand "sickle cell disease" to mean.
  - a. Do you think most people in this community understand what SCD is?
  - b. Do you know the difference between carrying a SCD trait versus having SCD?
- 2. Do you know anyone with (or who had) SCD?
- 3. Do you know how people get SCD?
- 4. Do you know what happens when someone has SCD?
- 5. Do you think that someone with SCD can live a normal life?
- 6. Do you know where people with SCD/their carers can access treatment?
- 7. Do you think it is challenging for people in this community to access healthcare? (Why or why not?)
  - a. Probe: Expenses?
  - b. Probe: Transportation?
- 8. When do you think people with SCD should be diagnosed?
- 9. Do you think that people with SCD face stigma in this community? (Why or why not?)
- 10. Any further comments?

Please thank the participants for their time.

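### The inactive-patient survey states no step for establishing sickle cell disease status, and its draft form presupposes a diagnosis, so reasons for non-use can mix diagnosed with undiagnosed or trait-only respondents

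*Protocol*

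**What the plan says.** Protocol Section 3.3 (Baseline patient survey) defines the inactive group as "individuals with SCD who do not access SCD care from the formal national health service". On how they are found, it says: "They will be identified through snowball sampling (by peer-SCD patients) and local community-based organisations who support SCD-affected persons". Section 3.5 adds "we will work through community-based organisations who provide support around SCD to whom these individuals may be known". Phone contact, consent and an interview follow. Enrolled respondents are then asked, by snowballing, "to determine if they may be aware of other SCD-affected persons/ carers of children living with SCD who are not receiving care". The target is 100 per country, and Table 1 shows 300 in total.

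Active respondents are described differently: "Those who are actively receiving care will be known to the three teaching hospitals that we are working with".

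On the draft inactive form in Appendix 1, item 5 reads "Participant/ dependent age of SCD diagnosis" and takes an age in months. Item 12, on stigma, again takes a diagnosis as given. In the background, Section 1.2 states: "At least 50% of individuals with SCD in SSA are never diagnosed and therefore do not take up care".

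**The concern.** The survey reports why people with SCD are not in care. At least three kinds of respondent could enter it: people diagnosed with SCD who do not attend, people who suspect SCD or were never tested, and possibly people told only that they carry the trait. Their reasons for not attending differ. The first group points to costs, distance, stigma or quality of care. The second points to a failure of detection. The third has no SCD to treat.

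The Aim in Section 3.1 names detection and implementation of care separately. Under Sections 3.3 and 4 the survey briefs the community and facility teams and feeds the initial programme theory in month 15. If the groups are pooled and cannot be told apart afterwards, the teams lose the information they need to choose between working on detection and working on access.

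**Working it through.** **1. The plan's own figure.** 100 per country × 3 countries = 300, which matches Table 1. No stated number is wrong; the issue is whom the 300 represent.

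**2. How SCD status is known, by route (Section 3.5).**

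| Group | Basis for SCD status |
|---|---|
| Active | Known to the teaching hospital |
| Inactive | Referral by an organisation or peer, then phone contact, consent and interview; no criterion, screening question or record check stated |

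Section 3.5 does write inclusion criteria for members of the community and facility teams, so the survey is the exception.

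**3. What the draft inactive form can record.**

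| Respondent or dependent | Item 5 (age at diagnosis) | Place in the tables |
|---|---|---|
| Diagnosed with SCD, not in care | Age in months | Correct |
| Suspected or never tested | No valid answer | Counted as not in care |
| Told trait only | Could give the age at which trait was found | Counted as not in care, not distinguishable |

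Items 6, 7, 12, 13 and 14 offer a don't-know answer and item 8 a not-sure answer; item 5 offers neither. No item asks whether, where or how SCD was diagnosed. Item 10, on reasons for not being in care, lists cost, transport, permission and an open category, so non-diagnosis could appear only as free text. Yet Section 1.2 treats it as a cause of non-use for at least half of people with SCD.

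**4. Illustrative size.** Everything in this step is assumed except the targets of 100 and 300. Let f be the share of respondents who are not diagnosed SCD cases, p1 the proportion of diagnosed respondents reporting a given barrier, and p2 the proportion among the others.

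Observed proportion = (1 − f) × p1 + f × p2, so the shift is f × (p2 − p1).

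With p1 = 60% and p2 = 20%:

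| f | Of 100 | Of 300 | Observed | Shift (points) | Enrolled to reach 100 diagnosed, 100/(1 − f) |
|---|---|---|---|---|---|
| 5% | 5 | 15 | 58% | −2 | 106 |
| 10% | 10 | 30 | 56% | −4 | 112 |
| 20% | 20 | 60 | 52% | −8 | 125 |
| 30% | 30 | 90 | 48% | −12 | 143 |

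With 60% against 40%, the shifts run from −1 to −6 points over the same range of f. With 50% against 0%, they run from −2.5 to −15.

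As a yardstick only, since this is not a probability sample, the 95% half-width at n = 100 and 60% is 1.96 × √(0.6 × 0.4 / 100) = 9.6 points. In the main illustration the shift exceeds this only at f = 30%.

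**The case against.** The case on the other side is substantial.

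- **Respondents identify themselves.** Referral only finds prospective participants. They are then phoned, consent, give an age at diagnosis and answer on stigma arising from it. A reader might infer that people are enrolled purely on a third party's word, but the text does not support that. What stands is that neither the referral nor the self-identification is checked, and no rule excludes someone who cannot answer item 5. The information sheets and consent forms were not in the text reviewed and might carry an eligibility line.
- **The form is a draft.** Section 3.3 expects changes, and Section 5.7 plans piloting so that answer categories are exhaustive. That could add an option to item 5. It would not by itself supply an eligibility rule or separate reporting.
- **Undetected people are largely out of reach of these routes.** Those unaware of having SCD will seldom be known to an SCD organisation, and detection is explored in the clinician focus groups and key informant interviews. This is fair, but it does not cover people who suspect SCD and are untested, whom peers or organisations may well refer.
- **The survey is exploratory.** Section 3.5 disclaims inference. This lowers the importance, but descriptive proportions still need a defined population.

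Two further inferences should be resisted. The focus group question "Do you know the difference between carrying a SCD trait versus having SCD" is put to general community members. It shows that the authors probe for confusion, not that they expect it among referred respondents. And the answer to item 7 for never having sought facility care also appears on the active form, where it hardly applies, so it looks like a shared answer list rather than a decision to admit undiagnosed people.

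**Conclusion.** The gap is real and of minor to moderate importance. As written, the inactive sample has no stated basis for SCD status beyond referral and implicit self-identification, and the form cannot record the non-diagnosis that Section 1.2 gives as a main cause of non-use. The results on reasons for non-use can therefore mix diagnosed people not in care with undiagnosed or suspected people, and possibly some with trait only. They cannot separate failure of detection from failure of uptake.

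The size is unknown. A reader might take the illustrative shifts as an estimate of bias, or expect the share who never sought care to be inflated by the full misclassified fraction. The documents support neither: f, p1 and p2 are all assumed, and inflation by the full fraction would need every misclassified respondent, and almost no true case, to give that answer. No inferential test or endpoint is affected. The harm is to the interpretation of the inactive group and of its contrast with the active group.

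**What to change.** Before item 5 on the inactive form, add one item about the patient or dependent:

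- (a) SCD diagnosed by a blood test, with place and age in months;
- (b) told by a health worker without a test;
- (c) suspected or never tested;
- (d) told carrier or trait only.

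Because the item concerns the patient or dependent, a carer who has the trait but looks after a child with SCD stays eligible. State in Section 3.5 that (d) is ineligible. Tabulate (a) and (b) separately from (c), and adapt item 12 so that it can be answered under (c). Whether (c) counts toward the 100 is the sponsor's choice, but it should be stated beforehand.

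Report that status is self-reported. Someone who mistakes trait for disease would still choose (a), so the item reduces misclassification without eliminating it.

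The cost is one item on a draft form, one eligibility sentence and one extra split in the tables, with no testing. Recruitment may be slightly slower; Section 3.5 already allows the target of 100 to be lowered if it cannot be met in the three months allotted.
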